5.4. Exploratory analyses of mechanisms of change

Change scores will be computed denoting changes in theoretical mechanisms measured using the questionnaires listed in pg. 7. These change scores will be computed between time-point 0 and time-points 6, and 12, denoting changes within the intervention phase.

Residualized change scores across multiple theoretical mechanisms will be entered into a Bayesian network analysis carried out separately for each intervention group, using the post-treatment (weeks 6, 12) PHQ-A as the dependent variable. Each Bayesian network will be trained using a Tree-Augmented Naïve Bayes (TAN) algorithm with adjustment for small cell counts (Friedman, Geiger, & Goldszmidt, 1997). This method offers a data-driven way to model a network of relationships (called attribute dependencies) between predictors and their joint influence over a target outcome (post-

treatment OLBI). TAN produces a simple and parsimonious network model where each predictor is allowed to depend on one additional predictor, thus modelling multiple two-way interactions. Variable selection will be performed using a 10-fold cross-validation procedure (Rodriguez, Perez, & Lozano, 2010). The resulting treatment-specific network models will be visualised using directed acyclic graphs (Shrier & Platt, 2008), which enable an intuitive interpretation of key mechanisms of change, their relative importance, and their interrelationships.

6. Ethical considerations

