Interventions	A 6-week, psychoeducation and physical education course consisting of online live psychoeducation sessions and physical activity sessions	
Randomization and data collection	Consenting participants will be randomly assigned to two groups; 1 and 2. Participants in both groups will be asked to complete outcome measures at an initial baseline assessment, after which only participants in group 1 will access a 6-week intervention (controlled phase). Next, group 2 will access the intervention during a 6-week period (full implementation phase). Finally, we will collect further outcome measures 6 months after both groups have completed the intervention (follow-up phase).	
Planned Sample Size	Minimum recruitment target of 192 participants, expecting 30% attrition.	
Data analysis method	 Trial data will be summarised using a CONSORT diagram and analyses will be based on intention-to-treat principles. The primary analysis will compare between and within-group differences in PHQ-A at baseline and 6 weeks, using ANOVA. Secondary analyses: between and within-group analyses will be conducted for GAD-7 and the physical activity measure at baseline and 6 weeks using ANOVA. Between-group and within-group effect sizes will be calculated using Cohen's d. Completion / dropout rates will be compared between groups using chi-square analysis. 	
Study Period	18 months (12 months active study period, plus 6 months analyses and dissemination)	

2. Background and rationale

Mental health problems cause huge public health burden in adolescents globally, as evidenced by a 20% prevalence (Belfer, 2008; World Health Organization (WHO), 2005). In the UK, the demand for Child and Adolescent Mental Health Services (CAMHS) services is at an all-time high and recent research shows children and young people referrals have increased by 26% in five years (Crenna-Jennigs & Hutchinson, 2018). Furthermore, 50% of children and young people that are assessed, wait more than 18 weeks to start treatment and over 3% wait over 12 months (Crenna-Jennings & Hutchinson, 2018).

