3.3. Hypotheses

- A) Exposure to the intervention will be associated with significantly lower mean score of depression and anxiety by comparison to a waitlist (delayed intervention) control group
- **B)** After the control group is exposed to the intervention, there will be no significant differences in mean depression and anxiety level between the two groups (immediate intervention group, delayed intervention group)
- C) Mean depression and anxiety severity for all participants at the end of the 6-month follow-up period will be significantly lower than baseline severity (prior to intervention), but not significantly different to end-of-treatment severity, indicating maintenance of gains
- **D)** Attitude towards physical exercise will significantly improve following the intervention, and be maintained at the 6-month follow-up period.

4. Study design

This will be a pragmatic, stepped wedge, open-label, randomised controlled trial. Consenting participants will be randomly assigned to two groups, by a research assistant using a computerized randomization algorithm (applying a simple 1:1 randomization schedule). Participants will take part in one of the two 6-week interventions, depending on their group assignment. They will complete an online survey with standardised measures at baseline (prior to starting the interventions), after 6 weeks (after group 1 has finished and prior to group 2 commencing), after 12 weeks (post-treatment) and finally after 6 months (follow-up). All measures will be completed online using an industry-standard survey system which automatically sends email reminders to consenting participants.

The interventions will be delivered using an online approach; weekly online video-conference sessions involving half an hour of psychoeducation and half an hour of physical activity. Both interventions will involve a total of six 1-hour sessions delivered once per week using video-conferencing software that can involve large groups of participants. The study will be carried out in four phases, which are illustrated in Figure 1.

[figure not shown]

Figure 1. Trial design and measurement time-points

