- The first prize draw will take place at the end of the 6-week intervention phase for each group (week 12 in Figure 1). To be eligible for inclusion in this prize draw, participants should have attended at least four intervention sessions and have completed the three online surveys up to that point. The prize will be a £20 Amazon voucher, and there will be one prize per participating site (trial site).
- The second prize draw will take place at the end of the 6-month observational phase (week 36 in Figure 1). To be eligible for inclusion in this prize draw, participants should have attended at least four intervention sessions and have completed all four online surveys. The prize will be a £50 Amazon voucher, and there will be one prize per participating site (trial site).
- In accordance with the University of Sheffield's policy for the ethical use of incentives in research, the prize winners will receive their electronic voucher code via email and they will be asked to return a signed receipt via email, which includes their name and work address, which is essential for auditing purposes and for legal reasons.

5. Statistical analysis plan

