5.3. Secondary analyses

ANCOVA (and sensitivity analyses) described above will be repeated at each of the time-points illustrated in Figure 1 (weeks 0, 6, 12, 36), using the PHQ-A, and using the GAD-A as an outcome, controlling for baseline scores. Outcomes at 6-months follow-up (pooled for both groups) will be compared to outcomes at the baseline assessment, using paired-samples t-tests (or an appropriate non-parametric test depending on the distribution of the data).

These analyses will be repeated at each of the post-intervention time-points illustrated in Figure 1 (weeks 6, 36), using the WEMWBS sub-domain scores. These between and within-group comparisons will also be summarised using effect sizes (Cohen's d).

Post-intervention measures (weeks 6, 36) will be compared to baseline measures (week 0) within each group, using paired-samples t-tests or an appropriate non-parametric test depending on the distribution of the data. Within-sample pre-post treatment effect sizes will also be computed using the method proposed by Minami et al. (2008).

We will carry out an exploratory analysis of knowledge and levels of activity before and after the intervention.

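### Section 5.3 tests group 2's week 6 score as post-intervention before group 2 has started the programme, and section 5.4 starts group 2's mechanism change at week 0

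*Protocol*

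**What the plan says.** The design text is clear about timing. In the Synopsis, both groups are measured at baseline, "after which only participants in group 1 will access a 6-week intervention (controlled phase"). The Synopsis continues: "Next, group 2 will access the intervention during a 6-week period (full implementation phase"). Section 4 places the second survey "after 6 weeks (after group 1 has finished and prior to group 2 commencing") and treats week 12 as the post-treatment survey.

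The analysis text uses other windows:

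- Section 5.3, within-group tests: "Post-intervention measures (weeks 6, 36) will be compared to baseline measures (week 0) within each group". The same section adds: "Within-sample pre-post treatment effect sizes will also be computed". It also repeats the between-group ANCOVA at weeks 0, 6, 12 and 36.
- Section 5.4, mechanism scores: "These change scores will be computed between time-point 0 and time-points 6, and 12, denoting changes within the intervention phase". The networks are "carried out separately for each intervention group, using the post-treatment (weeks 6, 12) PHQ-A as the dependent variable".

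**The concern.** For group 2, week 6 is the last survey before the programme and week 12 is the first one after it. Section 5.3 applies one list of post-intervention weeks to both groups. That list contains week 6 and omits week 12. Read as written, group 2's week 0 to 6 test would appear as a post-intervention result, although it describes the control period. Group 2's change by the end of its programme would have no within-group test. Hypothesis C refers to end-of-treatment severity for all participants, and for group 2 that can only be week 12.

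In section 5.4 the aim is to find mechanisms by which the programme acts. A predictor that measures change wholly or partly over the waiting weeks does not isolate that for group 2.

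**Working it through.** The plan gives no figure on this point to reproduce. The check sets each stated window against each group's programme weeks.

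**Inputs.** Group 1's programme runs over weeks 0 to 6 (Synopsis, section 4). Group 2's starts after the week 6 survey and lasts six weeks, so it runs over weeks 6 to 12 (6 + 6 = 12). The windows come from sections 5.3 and 5.4.

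**Formula.** For a window from a to b and a programme from s to e, programme weeks in the window = min(b, e) − max(a, s), and never less than 0.

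| Group | Window | Where stated | Calculation | Programme weeks |
|---|---|---|---|---|
| 1 | 0 to 6 | 5.3, 5.4 | 6 − 0 | 6 of 6 |
| 2 | 0 to 6 | 5.3; 5.4 read literally | 6 − 6 | 0 of 6 |
| 2 | 0 to 12 | 5.4 on either reading | 12 − 6 | 6 of 12 |
| 2 | 6 to 12 | not stated as a change window | 12 − 6 | 6 of 6 |

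**Two readings of section 5.4.** Read literally, both weeks apply to both groups, and group 2's 0 to 6 score is all waiting time. On the favourable reading, week 6 belongs to group 1 and week 12 to group 2. Group 1's window and group 2's end point are then right, but group 2's starting point is still six weeks before its programme. Section 5.3 has no such favourable reading, because week 12 is not in its within-group list.

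**Illustration only.** These values are assumptions, not figures from the protocol. Suppose the programme improves the mean by e = 0.5 SD (section 5.1 says only that a moderate effect is expected), and that scores improve by w = 0 to 0.3 SD per six weeks without any programme. Group 2's mean improvement would then be:

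- weeks 0 to 6: w = 0 to 0.3 SD, none of it due to the programme;
- weeks 6 to 12: w + e = 0.5 to 0.8 SD;
- weeks 0 to 12: 2w + e = 0.5 to 1.1 SD, of which w/(2w + e) = 0% to 0.3/1.1 = 27% arises in the wait.

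**The case against.** The strongest reply has four parts.

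1. *A week 0 to 6 comparison in group 2 is legitimate.* The Synopsis plans within-group comparisons at baseline and 6 weeks, and reporting the control arm's change is ordinary. This stands. What is wrong is the post-intervention label and the missing week 12 test, not the existence of the comparison. The effect-size sentence in 5.3 carries no week numbers, so by itself it does not exclude weeks 6 to 12.

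2. *The intervention phase in 5.4 may be a trial-level label for weeks 0 to 12.* Section 4.4 sets the first prize draw "at the end of the 6-week intervention phase for each group (week 12 in Figure 1"), and Figure 1, which shows the phases, is not available. This could excuse the label. It does not move group 2's starting point from week 0.

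3. *Section 5.4 is exploratory and unsettled anyway.* Section 4.3 lists no mechanism questionnaire, and 5.4 names two different target outcomes. This stands, and it is why the 5.4 part is the lesser one. It also means that any figure for how far the wait contaminates a mechanism score rests on assumptions from outside the protocol.

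4. *Comparing week 36 with week 0 follows hypothesis C*, which defines baseline as before the intervention. This stands, and that comparison need not change.

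A reader might also infer that the plan makes no use of group 2's programme period or of week 12. The protocol does not support that: the between-group ANCOVA is repeated at week 12 for PHQ-A and GAD-A, and the 0 to 12 change in 5.4 contains the programme weeks, mixed with the wait. What is missing is a change score for group 2 that starts at week 6.

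**Conclusion.** The point holds for the within-group analyses. In section 5.3 the rule as written is wrong for group 2: its week 6 test covers 0 of 6 programme weeks, and its end-of-programme survey is left out of the within-group tests. In section 5.4 the fault is milder. On the favourable reading, 6 of the 12 weeks in group 2's change score are waiting time. These counts follow from the protocol's own timetable and need no assumption; the SD figures above do, and are illustration only.

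A statistical analysis plan may exist, but this is not a detail that the protocol leaves open. It states the windows, and they conflict with its design.

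It would be tempting to conclude that the trial's main result is compromised. It is not: the primary analysis compares the groups with each other after group 1's programme, and there group 2's waiting weeks are the intended control. Sample size and delivery are also untouched. This is a modest correction to secondary and exploratory results, best made before data are seen so that nobody chooses among windows afterwards.

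**What to change.** - **Section 5.3.** Define the within-group pre-post tests and effect sizes as week 0 to 6 for group 1 and week 6 to 12 for group 2. Report group 2's week 0 to 6 change separately, as waitlist change. Keep the between-group ANCOVA time-points and the week 36 comparison with baseline.
- **Section 5.4.** Compute residualized change over each group's own programme period (weeks 0 to 6 for group 1, weeks 6 to 12 for group 2), with PHQ-A at the end of that period as the target. Separate networks by group can stay.

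**Cost.** The change is to wording and window definitions. PHQ-A and GAD-A are already planned at weeks 0, 6 and 12 in both groups, so they need no extra survey. For 5.4, the mechanism questionnaires and the target outcome have to be settled separately. Whichever questionnaires are chosen must be in the shortened surveys at weeks 6 and 12, which the change scores in 5.4 already require.

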6.1. Considerations about informed consent

This study requires NHS research ethics approval and it will require Health Research Authority (HRA) approval.

In order to obtain informed consent from participants and their guardians in line with good practice guidelines, we will take the following steps:

- Potential participants and their parent/guardian will be invited to contact a member of the research team if they have any further thoughts or questions after meetings and/or reading of the information leaflets. Contact details will be provided as part of the promotional materials described above.
- Potential participants and their parent/guardian will be advised of their right to withdraw from the study at any stage and the right to request their data to be deleted from the study dataset. This will be explicit in the electronic participant information sheet, in the consent form, and will be explained to participants following notification of randomisation. Each participant will receive an electronic copy of the information sheet and consent form via email, for their records.
- For those participants aged under 16 a parent/guardian will have to provide consent before the adolescent can participate
- For those participants aged 16-18 they can provide their own consent if they are deemed to have mental capacity. An information sheet will be provided for their parent/guardian to ensure they are aware of participation and what is required.

We will also be collecting fully anonymous data described above. We consider that our proposed method for aggregating and analysing fully anonymized data is congruent with the NHS information governance policy and good practice guidelines.

6.2. Potential for distress

Given the psychoeducational nature of the interventions, we do not envisage any potential for significant distress or adverse events. Nevertheless, participants will receive the contact details for the chief investigator in the information sheet, if they should wish to make a complaint or to raise any concerns about the intervention or conduct of the study. In the rare event that a participant should become distressed, they will be provided information by the research team about usual sources of psychological and or occupational health support available to employees in their NHS Trust.

Participants and their parent/guardian will also be provided with an information sheet listing support services that are available to them should any issues arise.

Participants will be made aware that if the research and/or delivery team become concerned about the welfare of a participant, or any abuse of the participants or someone else is disclosed we will have to break confidentiality. We will discuss this with the participant, but we may break confidentiality without their approval if we feel it is appropriate. Confidentiality will be broken by either referral to the GP or

emergency services depending on the severity and urgency, parents/guardians will also need to be informed.

7. Risk management

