4.1. Setting and participants

This study will involve adolescents aged 11-18 years old who are on a waiting list for CAMHS services, or have been highlighted by School Champions and School nurses, and are adolescents who would potentially benefit from some low level psychological intervention. The participants will live in the areas covered by RDaSH. Suitable participants should require low level intervention for support in;

understanding their emotions, coping with low mood, anxiety or stress, and learning strategies for improving their overall mental health and wellbeing.

Inclusion criteria

- Any child aged 11-17 (we will accept participants who turn 18 in the trial period) who may benefit.
- Children must attend a school within the Rotherham, Doncaster, North Lincolnshire or Bradford locality

Exclusion criteria

- Adolescents who are already in receipt of psychological therapy
- Adolescents with a diagnosed condition (such as Autism Spectrum Disorder, learning disabilities, severe depression)
- Adolescents experiencing suicidal ideation
- Adolescents with no access to electronic devices
- Anyone who has participated in either Home Goals or Safety Nets before
- Anyone who is 18 at the time of recruiting (we will accept if they turn 18 over the trial period but not before the trial starts)

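### The distress instruction in Section 6.2 points school pupils to support meant for NHS Trust employees

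*Protocol*

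**What the plan says.** Section 6.2 of the protocol covers distress and names four routes.

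- **Contact for complaints or concerns:** "participants will receive the contact details for the chief investigator in the information sheet".
- **Distress:** if a participant becomes distressed, the research team will give information about the usual psychological help and "occupational health support available to employees in their NHS Trust".
- **General support:** participants and their parents or guardians also receive an "information sheet listing support services that are available to them should any issues arise".
- **Welfare concern or disclosure of abuse:** "Confidentiality will be broken by either referral to the GP" or to emergency services, according to severity and urgency, and "parents/guardians will also need to be informed".

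Section 4.1 defines who can be in the trial. The age criterion is "Any child aged 11-17 (we will accept participants who turn 18 in the trial period) who may benefit". The school criterion is "Children must attend a school within the Rotherham, Doncaster, North Lincolnshire or Bradford locality". The synopsis likewise describes school attenders aged 11-18. No eligibility criterion mentions employment.

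**The concern.** The distress clause assumes that the participant works for an NHS Trust, whereas the eligibility criteria describe school pupils. A team member who followed the clause literally would give a distressed child information about services that the child has no entitlement to use.

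The population makes accurate signposting matter. Section 4.1 draws participants from CAMHS waiting lists and from school referrals, for help with low mood, anxiety or stress. Section 4.4 adds that taking part is not itself a CAMHS referral. Section 7.1, on risks to participants, contains nothing of its own and refers back, so Section 6.2 carries the protocol's content on this subject.

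The stake is participant safety wording. No effect on the trial's estimates or conclusions is claimed.

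**Working it through.** No sample size, power, alpha or rate enters this point, so there is no figure to reproduce. The check sets the text of the sections side by side.

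1. **Who the clause addresses.** In Section 6.2, the qualifier about employees and their Trust most naturally covers both the psychological and the occupational health support. Reading it more narrowly, so that it qualifies only the occupational health part, still leaves half the instruction addressed to employees.

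2. **Who is enrolled.** Under Section 4.1, participants are 11-17 at recruitment and must attend school in Rotherham, Doncaster, North Lincolnshire or Bradford. Some may turn 18 during the trial. None is recruited as a Trust employee. The clause and the population do not match.

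3. **Whether anything corrects it.** The sheet of support services is provided in addition to the employee information and is not stated to replace it. Section 7.1 only points back. No other section gives a different instruction for distress.

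4. **How many routes are affected.** Section 6.2 names four, as set out below.

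| Route in Section 6.2 | Stated trigger | Usable for a school pupil? |
|---|---|---|
| Chief investigator's contact details | Complaint, or concern about intervention or conduct | Yes |
| Employee support information | Participant becomes distressed | No |
| Sheet of support services | Any issue arising | Yes |
| GP or emergency referral, parents or guardians informed | Welfare concern or disclosure of abuse | Yes |

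   The count is 4 named − 1 unusable = 3 usable. The unusable route is the only one whose stated trigger is distress.

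5. **Likely origin.** Two other places in the current text also suit a workforce study. In Section 4.4, prize winners sign a receipt "which includes their name and work address". In Section 5.2, the sensitivity analysis adds a job-role covariate with administrative, mental health and other clinical categories. With the clause in Section 6.2, that makes three such phrases. They suggest carried-over text. This is an inference, and the mismatch in steps 1 and 2 stands without it.

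6. **Who would be covered.** The clause applies to any participant who becomes distressed. The recruitment target is at least 192, and Section 5.1 accepts further young people onto the trial without collecting their data; the clause would cover them too. The protocol gives no rate of distress, so no number affected can be derived.

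**The case against.** The best case on the other side concerns weight, since the mismatch itself is plain.

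- **The provision is largely made elsewhere in the section.** The sheet goes to the right people, sits under a heading about distress, and applies to any issue, which includes distress. The welfare route can also be reached through distress. This stands, and it limits the harm. It also means that the statement about the only distress-triggered route holds only in its literal sense: no other sentence names distress as its trigger. It does not mean that distress would otherwise go unanswered.

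- **Other text makes a wrong response less likely.** Section 4.2 has CAMHS and school nursing leading the psychoeducation half of each session, taken by trained clinicians, and Section 4.4 tells participants to reach CAMHS by the usual route. This also stands in part. Neither passage tells the research team what to do for a distressed participant.

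- **Literal compliance is hypothetical, and the fix adds no new service.** That is true. The protocol gives no sign that employee information would displace the sheet. But a protocol is written to be followed, and a safety instruction for minors should be one that staff can follow.

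- **Other carried-over phrases matter more for the analysis.** The job-role covariate does bear on a planned analysis, whereas this clause does not. That affects priority among corrections. It does not make the clause right.

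**Conclusion.** The concern holds. As written, the distress instruction in Section 6.2 cannot be applied to the population that Section 4.1 enrols, and nothing else in the protocol corrects it. It should be changed, although the gain is modest: one of four routes is unusable, three remain sound, and participants are not left without support. There is no effect on design, sample size or results.

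The conclusion rests only on reading the clause and the eligibility criteria as they stand. It needs no assumption about how often distress occurs or about where the wording came from.

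**What to change.** Replace the employee clause in Section 6.2. Suggested wording: if a participant becomes distressed, the research team will direct them to the services on the support sheet already given to participants and parents or guardians; where there is concern for the participant's welfare, the team will follow the GP or emergency referral route described in this section, with parents or guardians informed.

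The cost is one reworded clause that uses routes the section already names. Design, recruitment, data collection and analysis are unchanged.
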